17.1.2.4. PFS Censoring Rules (Set 4)

The PFS Censoring Rules (Set 4) are designed to address possible limitations of the scientific methods used for documentation of disease progression by including symptomatic or non-radiological disease progression as an observed PFS event.

Set 4 rules will be used for sensitivity analyses. Under Set 4 rules, an observed PFS event is defined as clinical (i.e., symptomatic or non-radiological) disease progression, documented disease progression, or death due to any cause. Subjects who do not experience clinical or documented disease progression or death during the analysis period will be censored.

PFS will be right-censored for subjects who meet one or more of the following conditions:

- Subjects with no post-baseline disease assessments (unless death occurred prior to the first scheduled assessment, in which case death will be considered a PFS event)
- Subjects who initiate subsequent anticancer therapy or intervention in the absence of documented progression
- Subjects who die or have disease progression immediately progression immediately after missing 2 or more consecutively scheduled disease assessment visits
- Subjects who are last known to be alive and progression-free on or before the data cut-off date

For such subjects, PFS will be right-censored according to the conventions described in Table H.H These conventions are based on the May 2007 FDA Guidance for Industry “Clinical Trial Endpoints for the Approval of Cancer Drugs and Biologics”.

Table H. PFS Censoring Rules (Set 4): Date of Progression or Censoring

Situation	Date of Progression or Censoring	Outcome
Death before first scheduled disease assessment	Actual date of death	Progressed
Death, documented disease progression or clinical progression between 2 scheduled disease assessments	The earliest of: (1) actual date of death, (2) actual date of first disease assessment showing clinical disease progression, (3) actual date of first disease assessment showing documented disease progression	Progressed
Missed ≥ 2 consecutive disease assessments immediately prior to a PFS event	Actual date of last non-missing disease assessment that is prior to the missed visits and prior to any PFS event	Censored
No death and no post-baseline disease assessments	Actual date of randomization	Censored
Non-protocol anticancer treatment started prior to any PFS event	Actual date of last non-missing disease assessment prior to start of non-protocol anticancer treatment	Censored
Alive and no PFS* event	Actual date of last non-missing disease assessment	Censored

**The definition of PFS event under Set 4 rules includes the situations categorized as “Progressed” in the table.*

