# **6 DISCONTINUATION**

## **6.1 Discontinuation of Individual Subject(s)**

A discontinuation is a subject who enrolled in the study and for whom study treatment is permanently discontinued prematurely for any reason.

The subject is free to withdraw from the study treatment and/or study for any reason and at any time without giving reason for doing so and without penalty or prejudice. The

investigator is also free to terminate a subject's involvement in the study at any time if the subject's clinical condition warrants it.

If a subject is discontinued from the study with an ongoing AE or an unresolved laboratory result that is significantly outside of the reference range, the investigator will attempt to provide follow-up until the condition stabilizes or no longer is clinically significant.

The subject will be discontinued from treatment if any of the following occurs:

- Subject develops objective disease progression per RECIST v.1.1 criteria based on investigator assessment.
- Subject develops clinical progression (if objective disease progression is not evaluated).
- Subject develops a Grade 4 or unacceptable AE as assessed by the Investigator (Refer also to Section 5.6.2.1.3 and Section 5.6.5.2.1)
- Investigator decides that it is in the subject's best interest to discontinue.
- Subject declines further study participation (i.e., study withdrawal).
- A significant protocol deviation or non-compliance occurs with a subject that compromises study objectives or subject safety.
- Subject is lost to follow-up despite reasonable efforts by the Investigator to locate the subject.
- The study is terminated by the Sponsor.

The Medical Monitor must be contacted before a subject is discontinued from study treatment for reasons other than objective disease progression per RECIST v.1.1.

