#### 7.4.1.2 Secondary Analysis

Sensitivity analyses will be performed to evaluate the robustness of the PFS results derived under the primary analysis ([Bhattacharya 2009](#), [Carroll 2007](#), [Stone 2011](#)). Such sensitivity analyses will assess potential sources of bias due to 1) differences between the planned and actual schedule of disease assessments, 2) censoring for subsequent anti-cancer therapy, 3) symptomatic or non-radiological disease progression, and 4) missed disease assessments due to reasons such as protocol deviations, consent withdrawal, and subjects lost to follow-up. The corresponding PFS results without stratification will be reported as supplemental analyses.

The same analyses of the primary PFS will be conducted using the PPS.

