17.3. OTHER EFFICACY VARIABLES

17.3.1. OTHER EFFICACY VARIABLES & DERIVATIONS

Tumor response and its components (target lesion response, non-target lesion response, timepoint response, and best overall response) were not clearly stated as analysis endpoints in the protocol; however, these measurements support the planned analysis endpoints and the protocol specified some supportive summaries and analyses which are described in this section.

Briefly, a disease assessment based on CT scan and/or MRI is planned every 8 weeks (± 7 days), counting from C1D1. Tumor response is determined using RECIST v 1.1 and recorded in the Disease Assessment eCRF. Best overall response is collected once per subject, on the Subject Status - Completion eCRF. A best response of CR or PR must be confirmed no less than 28 days after the criteria for response are first met.

Tumor response and best overall response are determined independently by the investigator and the central radiology reviewers. The central radiology review consists of assessment by 2 independent reviewers, followed by adjudication of the results if the 2 reviewers disagree. The primary and all secondary efficacy endpoints are based on these tumor response assessments plus any recorded subject death.

[Note: Clinical symptoms of disease progression are recorded as adverse events. Bone imaging scans and brain scans provide additional documentation of disease.]

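### Censoring Set 4 is meant to count clinical progression but does not reliably do so: it dates the event by a scan, gives early clinical progression no event row, and contradicts itself on new therapy

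*SAP*

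**What the plan says.** Protocol 7.4.1.2 commits to sensitivity analyses for four sources of bias in PFS, one of which is "symptomatic or non-radiological disease progression". SAP 17.1.4.3 assigns that check to Set 4, and SAP 17.1.6 relies on Sets 2 and 4 to examine non-informative censoring.

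SAP 17.1.2.4 says that Set 4 works "by including symptomatic or non-radiological disease progression as an observed PFS event". Under it, "an observed PFS event is defined as clinical (i.e., symptomatic or non-radiological) disease progression, documented disease progression, or death due to any cause". The detailed rules are these:

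- **Date.** For events between two scheduled disease assessments, Table H takes the earliest of three dates. The one for clinical progression is the "actual date of first disease assessment showing clinical disease progression".
- **Before the first scheduled assessment.** Table H has a Progressed row for death only. A subject who has not died and has no post-baseline assessment is censored at randomization.
- **New therapy.** The text censors "Subjects who initiate subsequent anticancer therapy or intervention in the absence of documented progression". The Table H row reads "Non-protocol anticancer treatment started prior to any PFS event".

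Four other places bear on this. Protocol 6.1 lists as a reason to stop treatment: "Subject develops clinical progression (if objective disease progression is not evaluated"). The Disease Assessment paragraph of the protocol synopsis and SAP 17.3.1 both describe a disease assessment as CT or MRI. SAP 17.3.1 adds: "Clinical symptoms of disease progression are recorded as adverse events". SAP 17.1.2 gives a tie-break for every censoring set: when more than one situation applies, Progressed takes precedence over Censored.

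**The concern.** In an open-label trial with an investigator-assessed endpoint, stopping for clinical deterioration without a scan is partly a matter of judgement. Set 1 does not count such a stop as an event: unless a scan-documented progression or a death later qualifies, the subject is censored. If these stops are more frequent in one arm, that censoring is informative and the hazard ratio shifts. Set 4 is there to show by how much.

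If the rules for Set 4 leave the same subjects censored, Sets 1 and 4 will agree partly by construction, and the agreement could be mistaken for robustness. Different programmers could also reach different event counts from the same text.

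**Working it through.** **Plan's own figure (background only).** With medians of 4 and 6 months, HR = 4/6 = 0.667. Events = 4 × (1.2816 + 0.8416)² / (ln 0.667)² = 18.03 / 0.1644 = 109.7, so 110, with power 80.1%. The critical HR is exp(−2 × 1.2816 / √110) = 0.783. These match SAP 3.5 and are not in dispute.

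**Step 1: the date.** Set 4 defines clinical progression as symptomatic or non-radiological and separates it from documented progression. Table H then dates it by an assessment that is elsewhere CT or MRI. Protocol 6.1 invokes clinical progression when objective progression has not been evaluated. A later scan that shows progression would be documented progression, which Table H lists separately. No other source is settled: SAP 17.3.1 places symptoms of progression among the adverse events, while Protocol 5.7.1 says progression itself is not reported as an adverse event, only its signs and symptoms. Set 2 (Table F) does name a workable date, that of the decision to discontinue treatment.

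**Step 2: before the first scheduled assessment.** The clinical-progression row covers only the interval between two scheduled assessments. If the screening scan counted as the first of these, the separate row for death before the first scheduled assessment would have no use, so the row appears to mean post-baseline assessments. Set 1 (Table E) has its own row for documented progression before the first scheduled assessment; Table H has no equivalent. A never-scanned survivor with clinical progression therefore meets a Censored row and no clear Progressed row. The tie-break needs two applicable situations, so it does not clearly help.

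**Step 3: new therapy.** Take a subject who progresses clinically, stops, then starts another drug. The text bullet says Censored, because progression was not documented. The Table H row does not apply, because the therapy followed a PFS event as Set 4 defines it. The tie-break also points to Progressed. The text and the table contradict each other.

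**Step 4: number of subjects.** The documents give no rate. Assuming 5% to 15%: 0.05 × 134 = 6.7 (7) and 0.15 × 134 = 20.1 (20). This is an upper bound on added events, since scanning continues after such a stop until new therapy (Protocol 5.5) and some subjects will become Set 1 events anyway. At 110 events only 134 − 110 = 24 subjects lack one, and those include subjects lost to follow-up and subjects still event-free.

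**Step 5: effect on the hazard ratio (illustration).** Simulated inputs: 134 subjects, 1:1; exponential PFS with medians 4 and 6 months; scans every 1.84 months (8 weeks); follow-up uniform from 6 to 24 months (assumed); unstratified Cox model; 2,000 replicates. A stated share of subjects progress only clinically. They are either counted at that time or censored at the last earlier scan (at about time zero if there was none).

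| Share, AGS-16C3F / axitinib | HR counted (events) | HR censored (events) |
|---|---|---|
| 5% / 5% | 0.669 (113) | 0.668 (107) |
| 10% / 10% | 0.661 (113) | 0.656 (101) |
| 15% / 5% | 0.661 (113) | 0.595 (102) |
| 5% / 15% | 0.662 (113) | 0.729 (101) |

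The unequal cases differ by 0.661 − 0.595 = 0.066 and 0.729 − 0.662 = 0.067. The censored column assumes that none of these subjects is ever counted, so the gaps are an outer limit for each assumed rate.

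**The case against.** The strongest reply is that Set 4's intent is plain. Its event definition names clinical progression, and Table H lists an assessment showing clinical progression apart from one showing documented progression. A sensible programmer would read the term loosely rather than leave that item empty. The text bullets refer to Table H for the censoring conventions, so the table can be taken to govern, and the tie-break supports it. The eCRFs are not among the documents, so a form may exist that records clinical progression with a date. Finally, Set 2 already counts every discontinuation without progression as an event on the decision date.

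Much of this stands. On new therapy it reduces the point to a contradiction that needs reconciling. A reader might infer that Set 4 operatively censors everyone who switches; the table and the tie-break do not support that. A reader might also infer that Set 4 adds no events and simply reproduces Set 1; that takes the narrowest reading of every rule and sets aside Set 4's own definition.

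The reply does not supply a date, and it does not give early clinical progression a Progressed row. Set 2 is no substitute: it also counts discontinuations for toxicity, withdrawal and any other reason, so a shift under Set 2 could not be attributed to clinical progression.

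**Conclusion.** The point holds as a defect in the rules of one sensitivity analysis. Table H ties clinical progression to a date that does not fit the event, gives clinical progression before the first scheduled assessment no clear event row, and conflicts with the Set 4 text on new therapy. The primary analysis, its alpha and the sample size are unaffected.

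The size is uncertain. The 7 to 20 subjects rest on an assumed rate and are an upper bound on added events. The effect on the hazard ratio is negligible at equal rates and about 0.07 in either direction at 15% versus 5%; that imbalance is assumed, and nothing in the documents predicts it.

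A reader might try to gauge early cases from the plan's medians: 1 − exp(−ln 2 × 1.84/4) = 27% on axitinib and 1 − exp(−ln 2 × 1.84/6) = 19% on AGS-16C3F fail by week 8. Those are all PFS failures, many of which the week-8 scan would document. They do not estimate how many subjects progress clinically without a scan.

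**What to change.** Four changes to SAP 17.1.2.4 and Table H:

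1. Date clinical progression as the date of the decision to end treatment when the recorded reason is clinical progression.
2. Add a row: *Clinical progression before first scheduled assessment; date of decision to end treatment; Progressed.*
3. Limit the bullet and row on absent post-baseline assessments to subjects with neither death nor clinical progression.
4. End the new-therapy bullet with *in the absence of documented or clinical progression*, so that it agrees with the table.

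The cost is SAP wording and minor programming. Set 2 already uses the decision date, SAP 15.1.1.2 takes it from the Subject Status – Completion eCRF, and SAP 9 tabulates the primary reason for stopping treatment. The sponsor should confirm that clinical progression is a selectable reason on that form and that the decision date is recorded in both arms; SAP 15.1.1.2 concerns AGS-16C3F only. If Set 4 has already been run, the change should be justified in the study report, as Protocol section 7 requires for departures from the SAP.

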17.1.3. PRIMARY ANALYSIS OF PRIMARY EFFICACY VARIABLE

The primary objective of this study is to test the hypothesis that PFS is superior (longer) for subjects treated with AGS-16C3F than for subjects treated with axitinib.

The primary analysis of PFS based on the investigator's assessment of disease will be performed in accordance with the ITT principle in the FAS. All subjects who undergo randomization will be included in the primary analysis and grouped according to the treatment groups assigned by randomization. The Censoring Rules (Set 1) which are presented in Section 17.1.2.1 will be used to derive the event status and PFS times.

The difference between treatment groups will be tested using a stratified log rank test at a one-sided 0.1 significance level. The stratification factors will be the ECOG PS and the number of prior systemic RCC regimens, without any other covariate(s). If the direction of the difference between treatment arms favors AGS-16C3F, then the observed significance level (p-value) of the 1-sided test of superiority of AGS-16C3F will be calculated as $0.5 * p$ -value from a two-sided log-rank test (corresponding to a chi-squared test with d.f.=1). If the direction of the difference favors axitinib, then the observed significance level will be calculated as $(1 - (0.5 * p\text{-value from the two-sided log-rank test}))$.

Kaplan-Meier survival curves for the primary analysis variable will be produced, overall and by stratum. The following descriptive statistics will be reported in a table, overall and by stratum:

- Progression status:
 - Number and percent of subjects with observed disease progression per RECIST
 - Number and percent of subjects who died without disease progression beforehand
 - Number and percent of censored subjects
- Number and percent of censored subjects, by reason for censoring
- Estimated progression-free survival time (months), including the minimum, 25th percentile, 50th percentile (median), 75th percentile, and maximum. The 2-sided 95% CIs for the 25th, 50th, and 75th percentiles, calculated using Greenwood's formula for the standard error, will also be reported.

The overall adjusted hazard ratio (HR) for AGS-16C3F relative to axitinib will be estimated using a proportional hazards (PH) model that includes terms for treatment effect and a stratification factor based on the baseline ECOG PS and the number of prior systemic RCC regimens (see section 7.1.1), and no other covariate. Ties will be addressed using Efron's (1977) method.

The model-based estimates for the HR and its corresponding one-sided 90% CI (upper confidence bound) will be reported. A two-sided 95% CI will also be reported in the clinical study report.

Hazard ratio estimates by stratum will be obtained from a PH model containing treatment, the stratification factor, and a treatment-by-stratum- interaction term. Homogeneity in the hazard ratios among strata will be examined by Wald's test. Results from a PH model without stratification will be reported also.

The adequacy of the model(s) will be evaluated, including an assessment of the proportional hazards assumption, as described in Section 17.1.6, "Exploratory Analyses".

17.1.4. SECONDARY ANALYSES OF PRIMARY EFFICACY VARIABLE

Sensitivity analyses will be performed to evaluate the robustness of the PFS results derived under the primary analysis (Bhattacharya 2009, Carroll 2007, and Stone 2011). Such sensitivity analyses will assess potential sources of bias due to 1) differences between the planned and actual schedule of disease assessments, 2) censoring for subsequent anticancer therapy, 3) symptomatic or non-radiological disease progression, and 4) missed disease assessments due to reasons such as protocol deviations, consent withdrawal, and subjects lost to follow-up.

17.1.4.1. Sensitivity to Analysis Set

Methods used for the primary analysis of the primary PFS endpoint will be used in the PPS to investigate the sensitivity to analysis set (i.e., sensitivity to major protocol deviations) and robustness of the primary analysis results. The Censoring Rules (Set 1) apply.

17.1.4.2. Sensitivity to Missing Data Assumptions

The Censoring Rules (Set 2) are designed to address the assumption of non-informative censoring and are presented in Section 17.1.2.2. After application of the Censoring Rules (Set 2), the same methods that were used in the primary analysis will be applied in the FAS population.

The Censoring Rules (Set 3) are designed to correct for potential bias due to any differences in the follow-up schedules for disease assessments (Section 17.1.2.3). After application of the Censoring Rules (Set 3), the same methods that were used in the primary analysis will be applied in the FAS population.

17.1.4.3. Sensitivity to Limitations in Scientific Methods

The Censoring Rules (Set 4) are designed to address possible limitations of the scientific methods used for documentation of disease progression by including symptomatic or non-radiological disease progression as an observed PFS event. After application of the Censoring Rules (Set 4), the same methods that were used in the primary analysis will be applied in the FAS population.

17.1.5. SUBGROUP ANALYSES OF PRIMARY EFFICACY VARIABLE

This study is not powered for statistical testing by subgroup. The interpretive focus of subgroup analyses will be on the descriptive statistics, point estimates, and confidence intervals by subgroup, rather than any within-group statistical tests.

The consistency of treatment effect across subgroups of subjects will be examined by repeating the primary analyses with replacement of the randomization stratification factor by a single planned covariate and its interaction with the treatment group variable. The planned covariates include age (≤ 65 , >65), gender (male, female), race (Caucasian, not Caucasian), ECOG Performance Status at baseline (0, 1), histology (clear cell, non-clear cell), number of prior treatment regimens for RCC (2 for clear cell or 1 for non-clear cell, >2 for clear cell or >1 for non-clear cell), and Heng's prognostic risk group (favorable, intermediate, poor). The subgroup levels of each covariate were defined in Section 7.6.

Hazard ratio estimates by subgroup will be obtained from a Cox PH model containing treatment, the subject characteristic of interest (i.e., the "covariate"), and a treatment-by-covariate interaction term. The model-based hazard ratio estimates for each level of the covariate and the adjusted hazard ratio (stratified by ECOG and number of prior regimens for RCC) from the primary analysis (main effect model), along with their respective two-sided 95% CI's, will be displayed on a Forest plot.

Subgroup analyses of secondary endpoints and/or secondary determinations are not planned.

17.1.6. EXPLORATORY ANALYSES OF PRIMARY EFFICACY VARIABLE

Section 17.4, "Subgroup Analyses", describes exploratory analyses related to the possible effects of selected covariates.

Analyses and plots which are generated for the purpose of validating statistical assumptions are also considered exploratory, and may be included or excluded from the clinical study report appendices at sponsor discretion.

Planned exploratory investigations of this nature include investigations of the censoring patterns and adequacy of PH models for the study data.

The assumption of non-informative censoring will be examined through sensitivity analyses with censoring rules sets 2 and 4. The censoring pattern will be assessed by reviewing the distribution of censoring times by treatment arm for differences between groups. Also, the cumulative percentage of censored subjects will be plotted against the observed censoring times, by treatment arm.

The models which are proposed for examination in this study include a (1) a PH model of treatment, stratified jointly for 2 randomization factors (primary analysis); (2) an unstratified PH model containing only a term for treatment; (3) a PH model containing terms for treatment and one covariate; and (4) PH models containing terms for treatment, a covariate, and treatment-by-covariate interaction. A total of 7 covariates will be examined; these are described in Section 17.4. Each covariate will be considered a time-fixed covariate (i.e., the values of the covariate cannot be written as a function of the survival time), categorical variable. If a PH model is appropriate, the hazard function $h(t|x)$ at time t given a vector of time-fixed covariate(s) will be proportional to the baseline hazard function $h_0(t)$ at t and the model will have a general form $h(t|x) = h_0(t) e^{(\alpha + x\beta)}$, where t is a subject's survival time, x is the vector of covariate(s) associated with the subject, h_0 is the baseline hazard function for an individual with $x=0$ for continuous variables and reference cell values of any categorical variable.

The proportional hazard assumption of the planned models will be assessed using suggestions from Therneau and Grambsch (2000) and Lawless (1982), as follows.

- The scaled Schoenfeld residuals for a covariate over event time will be calculated under each model. A plot of the scaled Schoenfeld residuals against event time should have a zero slope if the PH assumption reasonably holds for this covariate.
- A plot of log negative log survival function of the lifetimes versus the log of the lifetimes (i.e., $\log[-\log S_0(t|x_i)]$ versus $\log t$) within each level of x_i should produce roughly parallel lines if a Cox PH model is appropriate.

Further exploratory investigations of departures from the planned models may be conducted if suggested by the data. Exploratory analyses that are defined after database lock will be described in a separate requirements document.

